#### 1.2.3. Clinical Experience

This is a first-in-human study of U3-1402.

As of the 25 Aug 2018 data cut-off, 56 subjects had received U3-1402 as part of Study U31402-A-J101: 34 subjects in the Dose Escalation Part, 8 subjects in the Dose Finding Part, and 14 subjects in the Dose Expansion Part. At the time of the data cut-off, 41 subjects were receiving treatment, 13 subjects had discontinued treatment due to disease progression, 1 subject had discontinued treatment due to Grade 2 pneumonitis, and 1 subject had withdrawn consent.

Fifty-four (96.4%) of the 56 treated subjects had experienced at least 1 TEAE. All 54 subjects had also experienced at least 1 TEAE considered by the investigator as related to study drug. Among all treated subjects, the most frequent (>20%) TEAEs, all grades, regardless of causality

and noted in descending order of frequency, included nausea (47 subjects [83.9%]), decreased appetite (36 subjects [64.3%]), platelet count decreased (36 subjects [64.3%]), white blood cell count decreased (30 subjects [53.6%]), neutrophil count decreased (29 subjects [51.8%]), vomiting (25 subjects [44.6%]), aspartate aminotransferase (AST) increased (23 subjects [41.1%]), alanine aminotransferase (ALT) increased (22 subjects [39.3%]), anemia (19 subjects [33.9%]), stomatitis (17 subjects [30.4%]), alopecia (15 subjects [26.8%]), diarrhea (15 subjects [26.8%]), fatigue (12 subjects [21.4%]), and malaise (12 subjects [21.4%]).

Eighteen (32.1%) of the 56 treated subjects had developed treatment-emergent SAEs, including 12 subjects (21.4%) with study drug-related SAEs. The treatment-emergent SAEs, in descending order of frequency, included platelet count decreased (6 subjects [10.7%]); decreased appetite (3 subjects [5.4%]); and atelectasis, cellulitis, cholecystitis acute, dehydration, dyspnea, implant site infection, malaise, myalgia, pneumonia, pneumothorax, pseudomembranous colitis, thrombocytopenia, and urinary tract infection (1 subject [1.8%] each).

Additional data describing the clinical experience of U3-1402 are available in the current Investigator's Brochure.

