## **5.4.** Dose Interruptions and Reductions

Specific criteria for dose interruption, re-initiation, reduction and/or discontinuation of U3-1402 are listed in Table 5.2. Doses may also be interrupted for other AEs per Investigator discretion, and supportive therapy may be administered in accordance with local practice guidelines. All dose interruptions or dose modifications must be recorded on the AE and drug administration eCRF pages.

Dose modifications are applicable only to TEAEs that are assessed as related to use of U3-1402 by the Investigator(s). For non-drug-related TEAEs, follow standard clinical practice. Appropriate external experts such as a cardiologist, pulmonologist, etc, should be consulted as deemed necessary.

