	Grade 3 Prolonged (eg, not rapidly responsive to symptomatic medication and/or brief interruption of infusion); recurrence of symptoms following initial improvement; hospitalization indicated for clinical sequelae  Grade 4 Life-threatening consequences; urgent intervention indicated	Administration of U3-1402 should be discontinued immediately and permanently.  Urgent intervention indicated. Antihistamines, corticosteroids, epinephrine, bronchodilators, vasopressors, IV fluid therapy, oxygen inhalation etc, must be administered as clinically indicated.	
Fatigue/ Asthenia	Grade 3	Delay dose until resolved to ≤Grade 1 or baseline values, then:  If resolved to ≤Grade 1 or baseline values in ≤14 days, resume U3-1402.  If resolved to ≤Grade 1 or baseline values in >14 days, U3-1402 may be resumed after discussion and agreement reduce U3-1402 by 1 dose level and resume.	
Blood and lymphatic			
Neutrophil count decreased	Grade 3 (500 to <1000/mm  ; 0.5-1 × 10  /L)	Delay dose until resolved to ≤Grade 2, then resume U3-1402.	
a contract	Grade 4 (<500/mm  ; <0.5 × 10  /L)	Delay dose until resolved to ≤Grade 2, then reduce U3-1402 by 1 dose level.	

Table 5.2: Dose Delay Criteria and Dose Reduction for U3-1402 (Continued)

	Worst Toxicity NCI- CTCAE Version 5.0 Grade (unless otherwise specified)	Schedule Modification for U3-1402
Febrile neutropenia (ANC <1000/mm³;	Grade 3	Delay dose until resolved; then resume U3-1402. Consider reducing U3-1402 by 1 dose level.
<1 × 10  /L, fever >38.3°C or a sustained		Consider administration of granulocyte colony-stimulating factor as prophylaxis for all subsequent cycles and according to local guidelines.
temperature of ≥38°C for more	Grade 4	Delay dose until resolved, then reduce U3-1402 by 1 dose level and resume.
than 1 hour)		Administer granulocyte colony-stimulating factor as prophylaxis for all subsequent cycles and according to local guidelines.
Anemia	Grade 3 (Hemoglobin <8.0 g/dL)	Delay dose until resolved to ≤Grade 2 or baseline; then resume U3-1402.
		For recurrent anemia, delay dose until resolved ≤Grade 2 or baseline, then reduce U3-1402 by 1 dose level and resume.
		Consider packed red blood cell transfusion according to institutional guidelines.

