		
 
One blood sample collection for PK analysis as soon as ILD is suspected, if feasible
 

		Other tests, as clinically indicated
		If a noninflammatory/infectious etiology is confirmed by the Investigator, treat accordingly and resumption of U3-1402 may occur after discussion between the Investigator and Sponsor.
		All events of ILD regardless of severity or seriousness will be followed until resolution including after drug discontinuation.

Table 5.2: Dose Delay Criteria and Dose Reduction for U3-1402 (Continued)

	Worst Toxicity NCI- CTCAE Version 5.0 Grade (unless otherwise specified)	Schedule Modification for U3-1402
Pulmonary toxicity	Grade 1	The administration of U3-1402 must be delayed. U3-1402 can be restarted only if the event is fully resolved to Grade 0:
		
 
If resolved in ≤28 days from day of onset, maintain dose.
 

		• If resolved in >28 days from day of onset, reduce dose 1 level.
		Toxicity Management:
		
 
Monitor and closely follow-up in 2 to 7 days for onset of clinical symptoms and pulse oximetry.
 

		
 
Consider follow-up imaging in 1 to 2 weeks (or as clinically indicated).
 

		Consider starting systemic steroids (eg, at least 0.5-mg/kg/day prednisone or equivalent) until improvement, followed by gradual taper over at least 4 weeks.
		If worsening of diagnostic observations despite initiation of corticosteroids, then follow Grade 2 guidelines (if subject is asymptomatic, then subject must still be considered as Grade 1 even if steroid treatment is given).
	Grade 2	Permanently discontinue subject from study treatment. Toxicity Management:
		Promptly start systemic steroids (eg, at least 1-mg/kg/day prednisone or equivalent) for a minimum of 14 days or until complete resolution of clinical symptoms and chest CT findings, followed by gradual taper over at least 4 weeks.
		Monitor symptoms closely.
		Reimage as clinically indicated.
		
 
If worsening or no improvement in clinical or diagnostic observations in 5 days,
 

		
 
Consider increasing dose of steroids (eg, 2-mg/kg/day prednisone or equivalent) and administration may be switched to intravenous (eg, methylprednisolone).
 

		
 
Reconsider additional work-up for alternative etiologies as described previously.
 

		Escalate care as clinically indicated.

Table 5.2: Dose Delay Criteria and Dose Reduction for U3-1402 (Continued)

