	Worst Toxicity NCI- CTCAE Version 5.0 Grade (unless otherwise specified)	Schedule Modification for U3-1402		
Pulmonary toxicity	Grade 3 or 4	Permanently discontinue subject from study treatment.		
1 dimonary toxicity	Grade 5 of 1	Toxicity Management:		
		Hospitalization is required.		
		Promptly initiate empiric high-dose methylprednisolone IV treatment (eg, 500-1000 mg/day for 3 days), followed by at least 1.0 mg/kg/day of prednisone (or equivalent) for a minimum of 14 days or until complete resolution of clinical symptoms and chest CT findings, followed by gradual taper over at least 4 weeks.		
		Reimage as clinically indicated.		
		If still no improvement within 3 to 5 days,		
		
 
Reconsider additional work-up for alternative etiologies as described above.
 
		
		
 
Consider other immuno-suppressants and/or treat per local practice.
 
		
Endocrine disorders				
Endocrine	Grade 3	Delay dose until resolved to ≤Grade 2, then:		
disorders		If resolved in ≤14 days, resume U3-1402.		
		If resolved in >14 days, U3-1402 may be resumed after discussion and agreement between the Investigator and Sponsor.		
	Grade 4	Discontinue subject from U3-1402.		
Eye disorders				
Ocular	Grade 3	Delay dose until resolved to ≤Grade 2, then: If resolved in ≤7 days, resume U3-1402.		
		If resolved in >7 days, then reduce U3-1402 by 1 dose level.		
		Ophthalmologist consultation as clinically indicated.		
	Grade 4	Discontinue subject from U3-1402. Ophthalmologist consult as necessary.		
Renal and urinary d	isorders			
Creatinine increased	Grade 3 (>3.0 × baseline; >3.0 - 6.0 × ULN)	Delay dose until resolved to ≤Grade 1 or baseline, then reduce U3-1402 by 1 dose level.		
	Grade 4 (>6.0 × ULN)	Discontinue subject from U3-1402.		

Table 5.2: Dose Delay Criteria and Dose Reduction for U3-1402 (Continued)

	Worst Toxicity NCI- CTCAE Version 5.0 Grade (unless otherwise specified)  Schedule Modification for U3-1402		
Hepatobiliary disord	lers		
AST or ALT increased without TBL increased	Grade 2 (>3.0 - 5.0 × ULN if baseline was normal; >3.0 - 5.0 × baseline if baseline was abnormal)	Continue U3-1402. In subjects without liver metastasis, monitor AST/ALT 24 to 72 hours later, and continue regular monitoring until resolution.	
	if baseline was normal; >5.0 - 20.0 × baseline if	Delay U3-1402 dose until resolved to ≤Grade 1, then: If resolved in ≤7 days, resume U3-1402. If resolved in >7 days, then reduce U3-1402 by 1 dose level.	

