		It is strongly recommended to perform a full diagnostic workup, to exclude alternative causes such as viral or autoimmune hepatitis, alcoholic liver injury, biliary tract disorders, or hemodynamic abnormalities. Results from diagnostic workup (including, for example: INR, direct bilirubin, serologic tests for hepatitis A, B, and C; alcohol use, ultrasound, MRI, CT scan, concomitant medication use, immunoglobulin levels, ECHO) must be recorded within the eCRF.  If drug-induced liver injury is ruled out, the subject
		should be treated accordingly, and resumption of U3-1402 may occur after discussion between the Investigator and Sponsor. U3-1402 will be permanently discontinued if drug induced liver injury cannot be ruled out from diagnostic workup.

Table 5.2: Dose Delay Criteria and Dose Reduction for U3-1402 (Continued)

	Worst Toxicity NCI- CTCAE Version 5.0 Grade (unless otherwise specified)	Schedule Modification for U3-1402
AST or ALT> 3.0 × ULN (if liver metastases are present, >5 × ULN) with known Hepatitis B and/or Hepatitis C infection at		Delay U3-1402 until reactivation of Hepatitis B and/or Hepatitis C can be ruled out.  Perform HBV DNA and/or HCV RNA to rule out reactivation of Hepatitis B and/or Hepatitis C, respectively.  Hepatologist and infectious disease consultations are recommended.
baseline		If reactivation of Hepatitis B and/or Hepatitis C is confirmed, permanently discontinue U3-1402.
Gastrointestinal diso	orders	
Nausea	Grade 3 (Inadequate oral caloric or fluid intake; tube feeding, TPN, or hospitalization indicated)	Delay U3-1402 until resolved ≤Grade 1, and consider treatment with antiemetics and/or corticosteroids as per Investigators judgement and local practice/guidelines, then:  If resolved to ≤Grade 1 in ≤14 days, resume U3-1402.  If does not resolve to ≤Grade 1 in >14 days, reduce U3-1402 by 1 dose level.
Vomiting	Grade 3 (Tube feeding, TPN, or hospitalization indicated)	Delay U3-1402 until resolved ≤Grade 1, and consider treatment with antiemetics and/or corticosteroids as per Investigators judgement and local practice/guidelines, then:  If resolved to ≤Grade 1 in ≤7 days, resume U3-1402.  If does not resolve to ≤Grade 1 in >7 days, reduce U3-1402 by 1 dose level.
	Grade ≥4	Discontinue subject from U3-1402

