# 5.7. Subject Withdrawal/Discontinuation

#### 5.7.1. Reasons for Withdrawal

Any subject who discontinues from the study treatment for any reason will have their study treatment discontinuation recorded.

Subjects may be withdrawn from the study after signing informed consent for the following reasons:

- Progressive disease (PD) per RECIST version 1.1
- Clinical progression: provide date (ie, definitive clinical signs of disease progression, but a recent radiographic assessment did not meet the criteria for PD according to RECIST version 1.1)
- AE
- Death
- Pregnancy
- Withdrawal of consent by subject
- Lost to follow-up
- Protocol violation (specify)
- Study terminated by Sponsor
- Other, specify (eg, Investigator discretion)

If there is evidence that the subject is receiving benefit from treatment even though the subject has met a criterion for discontinuation as listed above, the subject may remain on study treatment after discussion with and approval from the Sponsor.

Discontinued subjects will be followed for survival, either through direct contacts or by collecting public records (eg, death certificates) as allowed by local laws.

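### The Section 5.7.1 exception lets any listed withdrawal reason be waived, pregnancy included, and should be limited to disease progression

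*Combined protocol and SAP*

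**What the plan says.** Section 5.7.1 gives ten reasons for which a subject may be withdrawn: RECIST progression, clinical progression, adverse event, death, pregnancy, withdrawn consent, loss to follow-up, protocol violation, study termination and other. It then adds that, given evidence of benefit and the Sponsor's approval after discussion, "even though the subject has met a criterion for discontinuation as listed above, the subject may remain on study treatment".

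Section 5.4 says "Specific criteria for dose interruption, re-initiation, reduction and/or discontinuation of U3-1402 are listed in Table 5.2". That table contains unconditional stops. For a Grade 3 or 4 infusion reaction: "Administration of U3-1402 should be discontinued immediately and permanently". For ILD/pneumonitis of Grade 2, and again for Grade 3 or 4: "Permanently discontinue subject from study treatment". Where the table wants the Sponsor involved in restarting, it says so. For a Grade 3 endocrine event that takes more than 14 days to resolve: "U3-1402 may be resumed after discussion and agreement between the Investigator and Sponsor".

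Section 5.8 lists conditions under which the subject should be discontinued. Item 2 is RECIST or clinical progression. Pregnancy is not on that list.

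**The concern.** The exception plainly suits one situation: a subject whose disease has progressed on imaging or clinically but who still seems to benefit. As written, it attaches to the whole list above it, so it also reaches reasons for which evidence of tumour benefit is no ground for further dosing. An Investigator and Sponsor who kept a pregnant subject on U3-1402 could cite Section 5.7.1 in support. With less force, so could those who continued dosing after a toxicity stop.

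What is at stake is subject safety. The payload is a topoisomerase I inhibitor, and Section 1.2.2.4 reports reproductive-organ toxicity in rats and ovarian findings in monkeys. Section 1.4 names ILD/pneumonitis as an identified risk. Section 15.9 marks a data and safety monitoring board as not applicable, so Sponsor approval is the only check that Section 5.7.1 itself names.

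**Working it through.** No arithmetic beyond counting applies. The check sets each stopping rule beside any text that limits the exception.

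**Scope.** There are ten listed reasons and none is excluded. By my judgement the exception makes sense for two (RECIST progression, clinical progression) and has no practical meaning for four (death, loss to follow-up, withdrawn consent, study termination). It is undefined for the other four (adverse event, pregnancy, protocol violation, other): 2 + 4 + 4 = 10.

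**Pregnancy.**

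| Place | What it does | Orders dosing to stop? |
|---|---|---|
| 4.2.1 item 10; 4.2.3 item 11 | Excludes pregnant women at entry | No |
| 4.1.1 item 10; 4.1.3 item 14; 5.6.4 | Requires contraception on study and for at least 7 months after the last dose | No |
| 8.7 | Foresees pregnancy while on drug; requires notification and outcome follow-up | No |
| Table 5.2; 5.8 | Do not list pregnancy | No |
| 5.7.1 | Names pregnancy as a possible reason for withdrawal | Permissive, and waivable by the exception |

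Pregnancy is thus named as a reason to stop in one place, and no other passage closes the exception to it.

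**Toxicity.** The Table 5.2 stops are not itemised in Section 5.7.1. They can enter only through the single adverse-event reason. Five entries use the word permanently: infusion reaction Grade 3/4, pulmonary Grade 2, pulmonary Grade 3/4, and the two hepatic rules, "U3-1402 will be permanently discontinued if drug induced liver injury cannot be ruled out from diagnostic workup" and "If reactivation of Hepatitis B and/or Hepatitis C is confirmed, permanently discontinue U3-1402". Other entries say discontinue without that word, for example confirmed myocardial infarction, Grade 4 QT prolongation and Grade 4 AST/ALT, bilirubin, creatinine or ocular events. The five are therefore not a full inventory of mandatory stops. None of these entries refers to Section 5.7.1, and Section 5.7.1 does not refer to Table 5.2.

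**Progression.** Section 5.8 item 2 says the subject should be discontinued; Section 5.7.1 says the same subject may continue. Items 1, 4 and 5 of Section 5.8 build in Sponsor discussion or discretion. Item 2 does not, so it cannot be read as already containing the exception.

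**A general limit.** Section 15.5 bars waivers of stated criteria. It does not settle the matter, because the exception is itself protocol text: using it is arguably compliance and not a waiver.

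**The case against.** The best defence is that specific text governs general text. The Section 5.7.1 list is permissive, so waiving an entry in it does not obviously waive a separate order in Table 5.2, which Section 5.4 designates as the specific criteria. The table is unconditional where it says stop and explicit where Sponsor-agreed restart is allowed. Section 5.8 item 3 adds that a significant adverse event should lead to discontinuation. Most of this stands. A reader might infer that the protocol authorises re-dosing after Grade 2 or worse pneumonitis or unresolved liver injury. The documents do not support that: Table 5.2 is the better reading, and what is missing is one sentence saying so.

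On pregnancy, the defence is that entry exclusion, on-study contraception and exposure-in-utero reporting all point against dosing. They do, and nobody could call continuation the protocol's intent. But they govern entry, prevention and reporting, and none tells a site to stop the drug.

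A reader might also count six statements that end treatment or participation at progression without mentioning the exception (two in the synopsis, then 3.1.1.4, 3.1.6, 5.6.3 and 5.8 item 2) and see six contradictions. A general duration rule followed by a later exception is not a contradiction, and the 5.6.3 text is a radiotherapy provision. Only 5.8 item 2 truly conflicts.

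Nor does the reported pneumonitis case measure the problem. Section 1.2.3 records that, among 56 treated subjects, "1 subject had discontinued treatment due to Grade 2 pneumonitis". That subject stopped as the table requires, so the case shows no override.

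Finally, safety data are monitored regularly (3.1.8), and SAEs, potential ILD and potential Hy's Law cases are reported within 24 hours (8.5). These reduce the risk of misuse but do not define the exception's limits.

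**Conclusion.** The point holds as a cheap improvement for patient safety. Ten withdrawal reasons fall under the exception and none is carved out. The substantive gap is pregnancy, where the only passage naming it as a reason to stop also lets it be waived. For toxicity there is an unstated order of precedence, with Table 5.2 most likely in control. For progression there is one direct conflict, 5.8 item 2 against 5.7.1.

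No efficacy endpoint is affected. PFS, for example, runs to the first documented radiographic progression or death, whatever dosing follows. The documents do not say how often the exception was used, and nothing suggests misuse. The conclusion rests on a literal reading of the phrase that ties the exception to the list above it, and on the absence of any limiting text elsewhere in the protocol.

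**What to change.** In Section 5.7.1, add wording such as: *This exception applies only to PD per RECIST version 1.1 or to clinical progression. It never applies to pregnancy, withdrawal of consent, or any discontinuation in Table 5.2, whether or not the entry says permanent.* In Section 5.8 item 2, add: *except as allowed in Section 5.7.1*.

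Because the Section 5.7.1 list is itself permissive, adding pregnancy to the Section 5.8 list would be a sensible optional step, giving sites a direct instruction to stop.

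The cost is a few lines in an amendment, with no new procedure, sample or analysis. The Sponsor loses discretion to continue dosing a benefiting subject after those stops, which is the purpose of the change. Treatment beyond progression remains available, as do the restarts that Table 5.2 already allows by agreement with the Sponsor.

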#### 5.7.2. Withdrawal Procedures

If a subject is withdrawn from the study, the Investigator will complete and report the observations as thoroughly as possible up to the date of withdrawal, including the date of last treatment and the reason for withdrawal.

If the subject is withdrawn due to an AE, the Investigator will follow the subject until the AE has resolved or stabilized as possible. All subjects who are withdrawn from the study and received study treatment should complete protocol-specified withdrawal procedures. Protocol-specified withdrawal procedures will involve an EOT visit and a F/U visit 28 days (- 7 days) after the last administration of U3-1402. Protocol-specified withdrawal procedures are the same as those to be performed at the EOT visit and the F/U visit (Section 6.7 and Section 6.8).

If the subject is withdrawn due to reasons other than death, withdrawal of consent, loss to follow-up, or study closure, and received study treatment, disease progression should be followed until PD or starting new anticancer therapy, whichever occurs first regardless of Follow-up period (Section 6.4.2).

If the subject is withdrawn due to reasons other than death, withdrawal of consent, loss to follow-up, or study closure, and received study treatment, follow-up for survival and subsequent anticancer therapy, if available (Section 6.9).

# 5.7.3. Subject Replacement

Subject replacement is not allowed for this study.

### **5.7.4.** Subject Re-screening Procedures

The study will allow re-screening for any subject who failed to meet eligibility criteria upon initial screening. A new Subject Number will be assigned at re-screening. The initial screening information and the reason why the subject was ineligible for the initial evaluation will be recorded on the Screening Log.

# **5.8.** Criteria for Suspending Study Treatment

The subject should be discontinued from the study under the following conditions:

- 1. If a subject is assessed as requiring a dose delay longer than 4 weeks (See Section 5.4), after discussion with the Sponsor.
- 2. If a subject is assessed PD (per RECIST version 1.1) or clinical progression by the Investigator.
- 3. If a subject presents any significant AE, as determined by the Investigator.
- 4. If any major protocol violation occurred, at the discretion of Investigator and Sponsor.
- 5. If becomes clear that the subject did not meet the inclusion/exclusion criteria, after discussion with the Sponsor.
- 6. If the subject withdraws consent.
- 7. If the study is terminated by the Sponsor.
- 8. At the discretion of Investigator, according to the condition of subject.

